**Assessment of nicotine dependence symptoms.** As part of Aims 1 & 2, participants will complete questionnaires assessing nicotine dependence symptoms, including CC dependence (Fagerström Test for Cigarette Dependence [FTCD; formerly the FTND; see Appendix C]), EC dependence (Penn State Electronic Cigarette Dependence Index [PSECDI; see Appendix J]), nicotine withdrawal (Minnesota Nicotine Withdrawal Scale-Revised [MNWS; see Appendix H]), affect (Positive and Negative Affect Scales [PANAS; see Appendix I]), and craving to smoke (Questionnaire of Smoking Urges-Brief [QSU-Brief; see Appendix N]) at each study visit.

During all phases, SMS/Qualtrics will be used to collect 2 daily random smartphone EMA measures of nicotine dependence symptoms, including nicotine withdrawal, craving, and affect, based on 8 items from the QSU, PANAS, and MNWS. Further details about the 2 daily smartphone EMA measures, as well as the once daily assessments of product use, are described above in the "Assessment of product use" section.

**Assessment of respiratory and other symptoms.** We will also assess respiratory symptoms at each visit using the American Thoracic Society questionnaire (ATSQ). The ATSQ is an 8-item questionnaire that assesses symptoms including coughing, wheezing, phlegm production, shortness of breath. An email will be sent to project staff when a participant completes the ATSQ and has a total score of >3 on questions #4-8. Staff will assess symptoms with the participant at the next visit. If symptoms present prior to the start of study product (V0 or V1), staff will add the conditions to the medical history. If the elevated score presents while on study product, staff will assess changes in symptoms and severity and log an adverse event, if indicated.

Study Medical Monitor [name] will oversee the collection, review, and attribution of adverse events (AEs) in this study and will consult with [name] on respiratory-

related AEs, as needed. The physician may delegate to other members of the medical team the task of a preliminary review of the adverse event, attribution, and recommended action plan. The physician will then complete the final review of the adverse event, confirm attribution and sign off on the adverse events.

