**Hypothesis Testing: Aim 1. To characterize the effects of switching to nicotine vs. placebo SRECs from CCs on product use, product acceptability, reinforcement, and nicotine dependence symptoms among adult daily CC smokers.** Assessments will include: product use (CPD, number of EC vaping sessions, nicotine, cotinine, minor tobacco alkaloids); product acceptability (explicit product liking, implicit product liking, and perceived product harm); reinforcement (RRE) and nicotine dependence symptoms (withdrawal, craving, and affect). We hypothesize that SREC-NIC will lead to decreases in CC-specific measures (CPD, minor tobacco alkaloids, and CC dependence), decreases in withdrawal symptoms, and increases in EC-specific use, acceptability, and reinforcement compared to SREC-PLA. The primary outcome measure for Aim 1 will be CPD.

**Hypothesis Testing: Aim 2. To characterize the differences between male and female CC smokers when switching to nicotine vs. placebo SRECs from CCs on product use, product acceptability, reinforcement, and nicotine dependence symptoms.** This aim will examine the moderating role of gender on the impact of SREC type on the assessments described in Aim 1. We hypothesize that men, compared to women, will show more product use, acceptability, and reinforcement with SREC-NIC, relative to SREC-PLA, but that women will show overall less SREC use, and less CC reduction, than men. The primary outcome measure for Aim 2 will be CPD.

**Exploratory Aim: To characterize which factors moderate or mediate the effects of switching to nicotine and placebo SRECs from CCs among male and female CC smokers.** In an exploratory fashion, we will examine whether baseline factors, including prior EC exposure and prior flavor preference, menthol CC preference, nicotine dependence, baseline TNE, and race/ethnicity, moderate the Aims 1 & 2 hypotheses. We will also examine the potentially mediating effects of product satisfaction, hormonal contraception use, menstrual phase, and smartphone-collected withdrawal, craving, affect, product use on these hypotheses.

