**Adverse experiences associated with specimen collection.** The collection of urine by the participants using specimen cups are not expected to result in adverse events.

**Adverse experiences associated with electronic cigarettes.** Use of ECs has been found to increase the risk of acute upper respiratory irritation, cough, phlegm production, headache, dry mouth/throat, vertigo, and nausea . Participants using SRECs, particularly the placebo version, may experience nicotine withdrawal effects, including increased irritability, difficulty concentrating, insomnia, anxiety, dysphoria, and hunger. None of these effects should result in serious adverse health consequences. However, it is possible that e-cigarettes may cause lung injuries or other serious health problems, which study medical monitor [name] and his team will monitor, along with our collaborator from the Department of Pulmonary Medicine, [name].

In the event of a new health risk associated with the electronic cigarettes used in this protocol that is identified, we will take the following steps: (1) the newly identified risk will be discussed within 5 days by study chair [name], collaborator and Study Physician [name], pulmonology collaborator [name], and collaborator [name] to determine its relevance to the study products used in this protocol; (2) if the risk is deemed by the collaborators to be related to the study products used in this protocol, we will contact all active subjects by phone within 5 days and submit a PI memo to MD Anderson's IRB and IND offices that describes this new health risk (also within 5 days); (3) Upon determination by the IRB, the protocol and ICD will be revised to incorporate information about the newly identified risk, the DSMB will be informed at the next semi-annual review of this protocol, and active participants will be reconsented with the details of these new risks. We will keep a log of any new risks communicated by the CDC and/or the Texas HHS that are deemed relevant to the study products used in this protocol, including participants who are contacted and/or reconsented and the date of this contact.

**Adverse experiences associated with questionnaires.** It is unlikely that completing questionnaires would lead to any potential risks for participants, although some participants may

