### ***Specific Instructions for Adverse Events Recording***

For this project, adverse events will be recorded according to the Recommended Adverse Event Recording Guidelines for Phase III protocols (see **Table 4**). Relevant medical history and baseline symptoms will be collected at the initial screening visit (V0) and V1, and will be graded according to the CTCAE 5.0 criteria and sent to the medical team for review. Any member of the medical team may review the medical history as part of the pre-randomization review process to clear the participant to V1. The study physician will complete a final eligibility review and sign-off prior to randomization. Adverse events will be recorded starting at every contact once the participant has started study product, which will be V2 and V3. In addition, the participant will complete a 30-day Adverse Event telephone assessment (30 days after V3, with a window of +/- 7 days) to follow up on any ongoing adverse events only.

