**Importance of the Knowledge to be Gained**

The potential benefit to society as a result of this study will be determine whether e-cigarettes serve as a potentially reduced risk nicotine product compared to combustible tobacco smoking in male and female adult smokers. This proposal will investigate gender differences in the impact of switching to e-cigarettes on adult combustible tobacco smokers, who are currently uninterested in quitting smoking, on a variety of domains, including product use, product acceptability, reinforcement, and nicotine dependence symptoms. These potential benefits outweigh the risks associated with the proposed research.

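### No comparison of respiratory symptoms or adverse events by SREC condition is planned, and grade 1 events go unrecorded, so mild airway effects would not be quantified by product

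*Combined protocol and SAP*

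**What the plan says.** **Respiratory symptoms.** Under Measures (assessment of respiratory and other symptoms), the 8-item ATSQ is given at each visit. The listed content includes cough, wheeze, phlegm and shortness of breath. It is the only entry under the respiratory heading of Table 2. The stated use is: "An email will be sent to project staff when a participant completes the ATSQ and has a total score of >3 on questions #4-8". Two follow-up steps are given. Before product: "If symptoms present prior to the start of study product (V0 or V1), staff will add the conditions to the medical history". On product: "If the elevated score presents while on study product, staff will assess changes in symptoms and severity and log an adverse event, if indicated".

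**Planned analysis.** The model in Statistical Approach & Expected Outcomes is introduced as the means of analysing the aims. The Aim 1 assessments are product use, product acceptability, and then "reinforcement (RRE) and nicotine dependence symptoms (withdrawal, craving, and affect". Aim 2 reuses that list with gender as moderator. The Exploratory Aim adds moderators and mediators, none of them respiratory.

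**Adverse events.** Under Specific Instructions for Adverse Events Recording, "adverse events will be recorded according to the Recommended Adverse Event Recording Guidelines for Phase III protocols". The rule itself is in Table 4. Events are recorded once product use has started, at V2 and V3.

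**Expected effects.** The section on adverse experiences with electronic cigarettes states: "Use of ECs has been found to increase the risk of acute upper respiratory irritation, cough, phlegm production, headache, dry mouth/throat, vertigo, and nausea".

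**The concern.** The protocol names airway symptoms as known effects of the product class. It measures several of them in each participant on usual brand, on SREC-NIC and on SREC-PLA. It then specifies no summary or comparison of those scores. The adverse event record cannot fill that gap for mild symptoms, because the adopted rule does not record grade 1 events.

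The risk is in interpretation. A respiratory adverse event count restricted to grade 2 and above could be read as showing no mild airway effect, when mild effects were excluded by rule. That matters because the section on the importance of the knowledge to be gained says the study will "determine whether e-cigarettes serve as a potentially reduced risk nicotine product compared to combustible tobacco smoking". If the ATSQ is analysed later without a prespecified plan, the choice of score, contrast and subgroup is open.

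**Working it through.** The plan states no figure on this point, so there is none to reproduce. The check has three parts.

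**1. Is the ATSQ in any planned analysis?** The paragraphs on product use, acceptability, reinforcement and dependence symptoms each tie their measures to Aims 1 and 2. The respiratory paragraph does not. The Aim 1, Aim 2 and Exploratory Aim texts name no ATSQ score, Health Changes Questionnaire item or adverse event rate. The Aim 2 model text refers to outcomes in general terms, but the ATSQ belongs to no aim.

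**2. What does the Phase III rule record?** Attribution rows with a Phase III entry in Table 4, by grade:

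| Grade | Rows recorded, of 5 |
|---|---|
| 1 | 0 |
| 2 | 3 (possible, probable, definitive) |
| 3 | 3 (same rows) |
| 4 | 5 |
| 5 | 5 |

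The total is 0 + 3 + 3 + 5 + 5 = 16 of 25 cells. This reads the blank grade 3 to 5 cells in the three related rows as merged with grade 2. Counting only cells that carry text gives 7 (three at grade 2, and two each at grades 4 and 5). The grade 1 count is 0 of 5 on either reading.

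**3. What could the data already collected show?** Inputs from Power and Sample Size: 140 completers of 164 randomised. As a lower value, the 77% retention reported for the team's current e-cigarette study gives 0.77 × 164 ≈ 126. The documents give no alpha, so two-sided 0.05 is assumed, with 80% power and a normal approximation.

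Detectable SREC-NIC minus SREC-PLA difference, in SDs of the within-person difference: (1.960 + 0.842)/√n.
- n = 140: 2.802/11.83 = 0.24
- n = 126: 2.802/11.22 = 0.25

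Gender by product interaction with equal groups, 2 × 2.802/√n: 0.47 (n = 140) and 0.50 (n = 126).

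In SDs of the score itself, multiply by √(2(1 − ρ)), where ρ is the assumed within-person correlation. At n = 140 this gives 0.28, 0.24 and 0.18 for ρ = 0.3, 0.5 and 0.7.

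The documents give no ATSQ SD, correlation or scoring, so nothing can be said in ATSQ points. Missed visits would reduce the number of complete pairs further. The plan expects only about 75% of sessions to be attended, but does not say how missed visits overlap within a participant.

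**The case against.** **Airway safety is not an aim.** The sentence after the reduced-risk statement limits the domains to product use, acceptability, reinforcement and dependence symptoms. That stands: the point concerns a secondary safety summary and does not touch the CPD analysis.

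**Would the trial fail to report airway harm?** A reader might infer this, but the documents do not support it. Grade 2 and higher events judged at least possibly related are recorded. All serious adverse events go to the IND Office whatever their attribution, the DSMB and IRB review safety every six months, and the medical monitor consults a respiratory collaborator. The gap is confined to mild effects compared by product.

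**Is the ATSQ only an absolute-score alert?** Only the trigger is absolute. After an on-product alert, staff assess change and log an event if indicated. Adverse events are also collected at V2 and V3 independently of the alert, and Table 2 adds a general Health Changes Questionnaire whose content is not shown.

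**Is there no usual-brand comparator?** That reading fails too. Baseline symptoms are collected at V0 and V1 and graded by CTCAE 5.0, and the ATSQ is completed at V1. An adverse event by definition begins with product, so the absence of a pre-product event count is not an omission.

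**ATSQ coverage is partial.** Throat symptoms and upper-airway irritation are not among its listed content. It can quantify cough and phlegm but may not cover everything the protocol lists as expected.

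**SREC against usual brand is a weak contrast.** Usual brand always comes first and is not randomised, and participants may keep smoking. This stands and limits the remedy.

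**Conclusion.** The point holds in a limited form. No comparison of the ATSQ or of adverse events by SREC condition is planned, and grade 1 events are unrecorded at every attribution. Mild cough, phlegm and similar effects would therefore not be systematically quantified by product, although the randomised within-person ATSQ data to do so will exist.

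The size is 0 of 5 grade 1 cells recorded, and an unused contrast able to detect about 0.24 to 0.25 SD of the within-person difference. Those SD figures show what the data could resolve. They do not measure harm, and they rest on the assumed alpha and on 126 to 140 complete pairs. The 16-of-25 count depends on the merged-cell reading; the grade 1 conclusion does not.

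A smaller matter needs reconciling. The alert depends on a fixed total on items 4 to 8, while the adverse event definition turns on a sign or symptom newly appearing or worsening. A rise to a total of 3 or less, or a rise on items 1 to 3 alone, sends no email. This is not proof that such events would be missed, because event recording does not depend on the alert.

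**What to change.** In Statistical Approach & Expected Outcomes, add a short secondary safety analysis:

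- Fit the ATSQ total in the existing within-person crossover model for the randomised SREC-NIC versus SREC-PLA contrast. Label the gender interaction exploratory.
- Summarise the ATSQ descriptively by phase, including the number of participants whose score worsened from their own V1 score.
- Summarise the Health Changes Questionnaire by phase, and adverse events by the product in use at onset.
- Label any comparison of SREC with usual brand as non-randomised and confounded with time and continued smoking.
- State beside any adverse event summary that grade 1 events were not recorded, by rule.

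Separately, the sponsor and medical monitor should reconcile the absolute ATSQ trigger in Measures with the adverse event definition in the section on adverse and serious adverse events. No alert or recording rule is proposed here.

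The cost is a paragraph of analysis text, one or two further models, a few descriptive tables and one sentence of caveat. It needs no new data, visits or participant burden.

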### Statistical Approach & Expected Outcomes

**General Data Analytic Strategy.** To analyze our aims, we will use a crossover design model with  $n = 140$  subjects (assuming 15% attrition of  $n=164$ ) and  $k = 3$  periods. In this design,  $t_0$  and  $t_1$  will be the two SREC types, with  $t_0$  for SREC-PLA and  $t_1$  for SREC-NIC. We will use the following model for  $y$  (e.g., CPD):  $y_{ij} = b_1 + b_{2t(i,j),t(l,j-1)} + e_{ij}$ , where  $b_1$  is the effect of subject  $i$ , and  $b_2$  is the effect of treatment  $t_{10}$  when preceded by treatment  $t_{10}$ .  $T(i,j)$  is the treatment assigned to subject  $i$  in period  $j$ , for  $1 \leq i \leq n$  and  $1 \leq j \leq k$ . The residual errors  $e_{ij}$  are assumed to be independent and identically distributed with expectation 0 and variance  $\sigma^2$ . In this design, each subject will act as its own control reducing the influence of confounding, reducing variance and improving accuracy and sensitivity for the estimated effect of interest. In the interaction models (Aim 2), gender will be entered in the equation and interacted with  $b_{2t(i,j),t(l,j-1)}$  to estimate gender by treatment interaction effects on all outcomes. Period and carryover effects will be evaluated by testing equivalence of effects across time (e.g., CPD collected using TLFB). We will utilize a mixed model approach for estimation using the "glmer" function of the "lme4" R package. Missingness will be treated as missing-at-random within maximum likelihood estimation and we will utilize not-missing-at-random approaches (e.g., pattern mixture model) if non-ignorable missingness is suspected. Given the large number of outcomes, the analyses will address issues of multiplicity by applying the False Discovery Rate.

**Hypothesis Testing: Aim 1. To characterize the effects of switching to nicotine vs. placebo SRECs from CCs on product use, product acceptability, reinforcement, and nicotine dependence symptoms among adult daily CC smokers.** Assessments will include: product use (CPD, number of EC vaping sessions, nicotine, cotinine, minor tobacco alkaloids); product acceptability (explicit product liking, implicit product liking, and perceived product harm); reinforcement (RRE) and nicotine dependence symptoms (withdrawal, craving, and affect). We hypothesize that SREC-NIC will lead to decreases in CC-specific measures (CPD, minor tobacco alkaloids, and CC dependence), decreases in withdrawal symptoms, and increases in EC-specific use, acceptability, and reinforcement compared to SREC-PLA. The primary outcome measure for Aim 1 will be CPD.

**Hypothesis Testing: Aim 2. To characterize the differences between male and female CC smokers when switching to nicotine vs. placebo SRECs from CCs on product use, product acceptability, reinforcement, and nicotine dependence symptoms.** This aim will examine the moderating role of gender on the impact of SREC type on the assessments described in Aim 1. We hypothesize that men, compared to women, will show more product use, acceptability, and reinforcement with SREC-NIC, relative to SREC-PLA, but that women will show overall less SREC use, and less CC reduction, than men. The primary outcome measure for Aim 2 will be CPD.

**Exploratory Aim: To characterize which factors moderate or mediate the effects of switching to nicotine and placebo SRECs from CCs among male and female CC smokers.** In an exploratory fashion, we will examine whether baseline factors, including prior EC exposure and prior flavor preference, menthol CC preference, nicotine dependence, baseline TNE, and race/ethnicity, moderate the Aims 1 & 2 hypotheses. We will also examine the potentially mediating effects of product satisfaction, hormonal contraception use, menstrual phase, and smartphone-collected withdrawal, craving, affect, product use on these hypotheses.

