**The NIDA SREC may not be as appealing as commercial ECs due to a lack of flavor options.** The SREC is currently available in one flavor, tobacco, which may not appeal to those with prior EC experience or a flavor preference. Most who have tried ECs or who use them routinely prefer flavors other than tobacco, with the most popular flavors being fruit flavors and candy/dessert flavors, with tobacco flavoring being among the least preferred flavor . Flavor preference is particularly strong among young adults , as 82.2% of current EC users reported using flavored (i.e., non-tobacco-flavored) ECs, compared to 69.3% of older adults . Additionally, NIDA SRECs are unavailable in menthol flavor, despite the significant number of menthol CC smokers, particularly among minority smokers . Thus, the availability of only tobacco-flavored NIDA SRECs may make them less appealing to CC smokers who have established flavor preferences. It is important to evaluate the SRECs among these users in order to provide a path for future research.

**Gender differences in nicotine reinforcement and nicotine withdrawal may influence EC use and acceptability.** There is evidence that men are more influenced by nicotine reinforcement than women. Male daily CC users smoke more than women and report greater nicotine dependence . However, even among samples of CC smokers who do not differ in smoking amount, men have been found to have higher nicotine levels than women , possibly due to men puffing  and inhaling  more than women. Men have been found to self-

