**Men and women may differ in their response to SREC product characteristics.**

Population-based survey studies examining gender differences in EC use have yielded equivocal results , although one small recent survey study found that female CC smokers who took up ECs were less likely to report completely switching to them than male smokers were . In terms of clinical trials methodology, there have been few published studies that have examined gender differences in response to EC exposure among adult CC smokers. A study exposing CC smokers to a nicotine-containing first generation "cigalike" ECs in the lab found that women rated it as more satisfying than men did . In a brief laboratory exposure to ECs following 1-hr of CC abstinence, men reported significant reductions in craving following nicotine (18 mg) EC use but not to placebo EC use, while women showed no difference by EC dose . In terms of flavor, there is preliminary evidence that women who were switched to ECs for a week with a non-preferred flavor produce lower nicotine concentrations and rate the EC as less likeable than men , suggesting that EC flavor may be more important to women in terms of EC use and acceptability. While these clinical trials studies are few and mainly preliminary, they are consistent with the CC literature reviewed above in that they suggest that men are likely to be more responsive to EC nicotine content than women, and that women are likely to be more influenced by non-nicotine factors, such as EC flavor acceptability and similarity of the EC vaping experience to CC smoking.

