Because of the absence of reliable effect sizes of the interaction effect under study in the literature, we estimated power for a series of effect sizes for both the direct and indirect effect. To perform the power analysis we first generated the matrix for our crossover design using the "samplingDataCRT" R package to sample data that reflects our prospective analysis. After generating the sample data, we calculated power for both the main effect of SREC type on CPD (Aim 1) and the SREC type by gender interaction (Aim 2) using three steps: 1) generate new CPD values from the crossover model defined above, 2) refit the model to the simulated data, and 3) evaluate the true positive success rate using the "simr" package . We ran 1000 simulations for each estimation for a series of effect sizes and for both the main effects and interaction models. **Figure 2** presents the power curves of these analyses. For the gender by SREC type interaction (Aim 2), **Figure 2** indicates that we have 80% power to detect a difference of 3.5 CPD or larger between the genders during SREC-NIC. For the SREC type main effect (Aim 1), **Figure 2** (inset) indicates that we have 80% power to detect a difference of 1.75 CPD or larger between SREC-NIC and SREC-PLA. The minimal detectable effect size is larger for the interaction effect compared to the main effect due to the increased power required to detect subgroup effects in randomized trials . Since the main modeling framework is linear, the interaction effect under study has an additive interpretation, such that the combined effects of SREC-NIC and being male contributes more to CPD reduction than the individual effects of the two factors. Additive interaction effects are more relevant for public health decision making and require a lower sample size than multiplicative interaction effects . In conclusion, our proposed sample size of 140 provide enough power to detect a CPD change of 1.75 for the main effect of SREC type and a CPD reduction of 3.5 for the proposed interaction effect, which we believe will be adequate to detect the likely differences we would observe.

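### Does the absolute-scale gender by SREC interaction in Aim 2 need a baseline-CPD or ratio-scale companion analysis?

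*Combined protocol and SAP*

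**What the plan says.** The Aim 2 model is described in Statistical Approach & Expected Outcomes: "In the interaction models (Aim 2), gender will be entered in the equation and interacted with" the treatment term, "to estimate gender by treatment interaction effects on all outcomes". CPD is the primary outcome. Under Hypothesis Testing: Aim 2 the expectation is that "women will show overall less SREC use, and less CC reduction, than men".

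Power and Sample Size fixes the scale: "Since the main modeling framework is linear, the interaction effect under study has an additive interpretation". It explains this as meaning that "the combined effects of SREC-NIC and being male contributes more to CPD reduction than the individual effects of the two factors", and justifies the choice: "Additive interaction effects are more relevant for public health decision making".

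Two statements in the Review of Relevant Literature bear on interpretation. One is that "Male daily CC users smoke more than women and report greater nicotine dependence"; the other is that "men are likely to be more responsive to EC nicotine content than women".

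The Exploratory Aim lists nicotine dependence and baseline TNE among the moderators of the Aims 1 and 2 hypotheses. No section names an interaction of baseline CPD with SREC type, or a log or ratio model of CPD.

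**The concern.** Subject effects in a crossover remove differences in smoking level between people. They do not remove a treatment effect that is proportional to that level. If nicotine lowers CPD by the same percentage in men and women, and men start higher, the absolute nicotine-placebo difference is larger in men, which is the hypothesised direction. A significant interaction could then be taken as evidence that men respond more to nicotine, the rationale given in the literature review, when it reflects only heavier smoking. Nothing in the design balances baseline CPD between the sexes: Table 1 admits anyone who smoked in the past 30 days, and randomization is stratified by gender alone. Gender is the trial's central question, so the interpretation of this test matters.

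**Working it through.** **Inputs from the documents.** Analysed n = 140, taken as 70 per gender; 80% power at 1.75 CPD for SREC type and at 3.5 CPD for the interaction (Power and Sample Size). No SD and no alpha are stated, so two-sided 5% is assumed.

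**Inputs assumed.** Mean baseline 15 CPD, between-person SD 8, male-female gap of 2, 4 or 5 CPD, and equal proportional effects in both sexes.

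**1. The plan's own figures.** Let s be the SD of the within-person nicotine-placebo difference.
- Main effect: s = 1.75 × √140 / (1.96 + 0.84) = 7.39.
- Interaction: s = 3.5 / (2.80 × √(2/70)) = 7.39.

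The two detectable differences agree with each other. With the t distribution on 138 df, s = 7.34, a residual SD of 7.34/√2 = 5.2. The 80% itself cannot be confirmed independently, because the SD is solved from it.

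**2. Size of the artefact.** Let f be the proportional reduction on nicotine minus that on placebo, the same in both sexes. The nicotine-placebo difference is then −f × baseline, so the additive interaction has magnitude f × gap. The SD of the difference becomes √(7.34² + (8f)²).

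**3. Rejection rate when proportional response is identical (noncentral t, 138 df).**

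| f | Gap 2 | Gap 4 | Gap 5 |
|---|---|---|---|
| 0.117 (= 1.75/15) | 0.23 CPD, 5.4% | 0.47 CPD, 6.6% | 0.58 CPD, 7.5% |
| 0.30 (assumed) | 0.60 CPD, 7.4% | 1.20 CPD, 15.0% | 1.50 CPD, 20.7% |
| 0.46 (assumed, 96% against 50%) | 0.92 CPD, 10.1% | 1.84 CPD, 26% | 2.30 CPD, 37.7% |

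Using the 16.2 CPD starting level of the cited switching study instead of 15 gives f = 1.75/16.2 = 0.108 and artefacts of 0.2 to 0.5 CPD.

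**4. When it starts to matter.** Rejection reaches 10% only at f of about 0.46, 0.21 or 0.17 for gaps of 2, 4 or 5 CPD. These are nicotine-placebo differences of about 6.8, 3.1 or 2.5 CPD, all above 1.75. To produce a spurious 3.5 CPD interaction at f = 0.30 the gap would have to be 3.5/0.30 = 11.7 CPD.

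**5. What companion models would give.**
- A model of Phase 2 and 3 CPD with Phase 1 CPD × SREC type added brings rejection to 4.1–5.4% in simulation if Phase 1 CPD has little error. At error SD 5.2 about 30% of the artefact remains. It compares men and women at equal baseline smoking, which is not the stated hypothesis.
- A log-link model has a standard error of 0.13 to 0.19 for the log ratio of ratios. For 80% power it needs a ratio of exp(2.80 × 0.13) = 1.44 to exp(2.80 × 0.19) = 1.70. It also has the opposite bias: an equal 5 CPD drop from 17 and from 13 gives ratios 12/17 = 0.71 and 8/13 = 0.62, an apparent female advantage with no difference in absolute response.

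**The case for a change.** The best case for a change is that the gap and the proportional effect are unknown, so nobody can say in advance that the small cases apply. The one percentage reduction cited for sizing is 96.3%. The data are already collected, and a supportive model would cost only wording and little precision: the standard error of the interaction goes from 1.26 to at most 1.29 at the 1.75 CPD effect with a gap of 4, and a real 3.5 CPD interaction keeps 79–80% power when there is no gap. A positive result will invite the question of whether it is just heavier smoking, and an answer fixed beforehand is more convincing than one found afterwards.

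Part of this stands. The additive test alone does not show greater male response at equal smoking level, and neither dependence nor TNE is the same thing as baseline CPD.

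It does not make the plan unsound. The sentence about being male explains what an additive interaction is; it makes no claim about nicotine sensitivity net of smoking level. The moderator list is introduced as open-ended, and the two measures it names both track smoking intensity. The interaction is also fitted to outcomes such as liking and perceived harm, which need not scale with CPD. If the three periods of the model include Phase 1, as the three-phase design suggests, CPD by gender on usual brand, placebo and nicotine follows from the planned fit, so the gap and the percentage reductions will be visible.

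**Conclusion.** No change is needed. The planned interaction is a valid test of a gender difference in absolute CPD effect, which is what Aim 2 hypothesises, and the choice of scale is stated and argued. Each scale has its own artefact, so the choice is a fair trade-off.

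At the 1.75 CPD effect the artefact is 0.2 to 0.6 CPD, with 5.4% to 7.5% rejection. It is material only if the nicotine-placebo difference and the gender gap are both large. The protocol's remarks that dual users reported nearly a 50% reduction and that SREC uptake may be low point toward the smaller cases. The statement that men smoke more concerns daily smokers, while Table 1 also admits non-daily ones. With no gap, or with equal absolute reductions, nothing remains.

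These sizes rest on the assumed mean, SD, gaps and equal-percentage premise, none of which the documents supply. A careful analyst would in any case report Phase 1 CPD by gender and describe a positive result as a difference in absolute cigarettes per day.
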